#### 2.6.4.2. Exploratory Immunogenicity Endpoints

The below exploratory analyses of immunogenicity may be performed:

- GMT and GMFR (compared to Day 1) to vaccine mismatched strains at all evaluable time points

- GMT and GMFR (compared to Day 1) to vaccine matched and mismatched strains assayed by alternative methods (including but not limited to: microneutralization assay for influenza or ligand-binding assay for SARS-CoV-2) at all evaluable time points
- Frequency, magnitude, and phenotype of virus specific T-cell and B-cell responses measured by flow cytometry or other methods, and to perform targeted repertoire analysis of B cells and T cells after vaccination
- Frequency, specificities, or other endpoints to be determined for the further characterization of immune responses

## **2.6.5. Exploratory Analysis**

### **2.6.5.1. Efficacy Analysis**

While the study will not be powered for efficacy assessments, symptoms of infection with respiratory pathogens will be tracked as an exploratory objective in this study (Part 1 only). Efficacy analyses will be performed on the FAS. Frequency of RT-PCR-confirmed protocol-defined influenza-like illness (ILI) and RT-PCR-confirmed symptomatic SARS-CoV-2 observed among the participants in the FAS will be summarized according to the vaccination groups as randomized.

### **2.6.5.2. Influenza Infection**

A protocol-defined ILI is determined by the occurrence of at least 1 respiratory illness symptom concurrently with at least 1 systemic symptom, or the occurrence of any 2 or more respiratory symptoms, as shown in Table 8.

An RT-PCR confirmed protocol-defined ILI is defined as a positive influenza result on a respiratory sample by RT-PCR performed at the Global Central Laboratory and/or a local certified laboratory within 7 days of onset of protocol-defined ILI at any time during the study period.

**Table 8 Respiratory and Systemic Symptoms for Protocol-defined ILI (Part 1)**

Respiratory symptoms	Systemic symptoms
Sore throat Cough/rhinorrhea/nasal congestion ( $\geq 1$ of the 3 symptoms count as 1 respiratory symptom) Sputum production Wheezing Difficulty breathing	Body temperature $\geq 37.5^{\circ}\text{C}$ [ $\geq 99.5^{\circ}\text{F}$ ] Chills Tiredness Headache Myalgia Nausea/vomiting Diarrhea

Derivation of PT-PCR confirmed protocol-defined ILI:

The eligible protocol-defined ILI symptoms will be documented on the ILI symptom assessment eCRF. The following derivation steps will be performed on each participant to determine whether protocol-defined ILI occurred within the specified window based on positive RT-PCR results:

Step 1: The time window for protocol-defined ILI to be considered as RT-PCR confirmed will be calculated based on each positive RT-PCR collection date  $\pm 7$  days (ex: positive RT-PCR collection date – 7 days through positive RT-PCR collection date + 7 days).

Step 2: Within this time window, determine the earliest eligible symptoms for protocol-defined ILI. Considering the symptoms listed in (Table 8) that onset within the positive RT-PCR collection date window from Step 1, eligible symptoms are defined as those that meet either of the criteria given below, based on their start and end dates:

- The occurrence of at least 1 respiratory illness symptom and at least 1 systemic symptom that overlap for at least 1 day or
- The occurrence of any 2 or more respiratory symptoms that overlap for at least 1 day.

Step 3: The start date for the RT-PCR confirmed protocol-defined ILI will be set as either the positive RT-PCR date or the earliest eligible symptom onset date, whichever occurs earlier.

The following summaries will be provided for influenza infection:

- The number and percentage of participants with an RT-PCR test results (Positive, Negative, Not Applicable, Missing) at Baseline will be summarized by vaccination group (as defined in Section 2.6.1).

- The number and percentage of participants with an RT-PCR test results (Positive, Positive and <=14 Days After Injection, Positive and > 14 Days After Injection, Negative, Not Applicable, Missing) excluding Baseline will be summarized by vaccination group (as defined in Section 2.6.1).
- The number and percentage of participants with RT-PCR confirmed protocol-defined ILI within the period starting from 14 days post-injection up through EoS will be summarized by strain of influenza virus, and by time period. A 2-sided 95% CI using the Clopper-Pearson method will be provided for the percentage of participants with the RT-PCR confirmed influenza infection.
- The number and percentage of participants with RT-PCR confirmed protocol-defined ILI within the period starting from 14 days post-injection up through EoS will be summarized by respiratory symptoms and systemic symptoms
- A listing presenting the RT-PCR test results for influenza will be provided.
- A listing presenting the symptom assessment for protocol-defined ILI will be provided.

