#### 10.3.7. Influenza-Like Illness

A protocol-defined ILI is determined by the occurrence of at least 1 respiratory illness symptom concurrently with at least 1 systemic symptom or the occurrence of any 2 or more respiratory symptoms as defined below.

Respiratory Symptoms	Systemic Symptoms
Sore throat	Body temperature $>37.2^{\circ}\text{C}$ ( $>99^{\circ}\text{F}$ )
Cough/rhinorrhea/nasal congestion ( $\geq 1$ of the 3 symptoms count as 1 respiratory symptom)	Chills
Sputum production	Tiredness
Wheezing	Headache
Difficulty breathing	Myalgia
	Nausea/Vomiting
	Diarrhea

A CDC-defined ILI is defined as body temperature  $\geq 37.8^{\circ}\text{C}$  ( $100^{\circ}\text{F}$ ) accompanied by a cough and/or sore throat.

An RT-PCR-confirmed ILI is defined as a positive influenza result by RT-PCR done at any setting during the study period.

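### SAP Table 8 sets the temperature item of protocol-defined ILI at 37.5°C or above, protocol 10.3.7 at above 37.2°C, and SAP Section 4 declares no change

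*SAP*

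**What the plan says.** Protocol Section 9.5.2 plans, for Part 1 only, a summary in the Full Analysis Set of how often RT-PCR-confirmed protocol-defined ILI occurs, by randomized group. Protocol Section 10.3.7 defines the term. A participant qualifies with "at least 1 respiratory illness symptom concurrently with at least 1 systemic symptom or the occurrence of any 2 or more respiratory symptoms", and one of the systemic symptoms is "Body temperature $>37.2^{\circ}\text{C}$ ( $>99^{\circ}\text{F" (above 37.2°C, above 99°F). On confirmation the same section says: "An RT-PCR-confirmed ILI is defined as a positive influenza result by RT-PCR done at any setting during the study period". It also carries a second, separately named definition, beginning "A CDC-defined ILI is defined as body temperature", with a threshold of 37.8°C.

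SAP Section 2.6.5.2 takes over the protocol's name and its combination rule. Its Table 8, titled as the symptom list for protocol-defined ILI, gives the temperature item as "Body temperature $\geq 37.5^{\circ}\text{C}$ [ $\geq 99.5^{\circ}\text{F" (37.5°C or above, 99.5°F or above). All other respiratory and systemic symptoms in Table 8 are those of protocol 10.3.7.

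SAP Section 4 states that nothing in the planned analysis has changed. SAP Section 1 says the SAP governs where its methods differ from the protocol's. Protocol Section 9 asks that changes to exploratory analyses be listed, with when and why, in the SAP or the clinical study report (CSR).

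**The concern.** One name carries two thresholds. A reader of the Part 1 report who sees a row for protocol-defined ILI will look up protocol 10.3.7 and take the row to have been counted that way. Under Table 8 it was not: a mild temperature elevation that the protocol accepts as a systemic symptom is ignored. SAP Section 4 gives the reader no warning. At stake are the accuracy of a label and of a declaration and, possibly, a few cases in an exploratory count.

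**Working it through.** **1. Is it a conversion slip?** Using °F = °C × 9/5 + 32:
- Protocol: 37.2 × 9/5 + 32 = 98.96, which rounds to the stated 99°F.
- SAP: 37.5 × 9/5 + 32 = 99.5, exactly as stated.

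Each document agrees with itself, so the thresholds really differ. The SAP value is not the 37.8°C of the protocol's other ILI definition either.

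**2. Which readings are classified differently?** To one decimal, 37.3 and 37.4°C (99.1 to 99.4°F) count under the protocol and not under the SAP. All other readings are treated alike.

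**3. Who is reclassified?** Hold every other SAP rule fixed, assume a positive RT-PCR inside the SAP window with overlapping symptoms, and change only the temperature cell:

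| Symptoms | Item above 37.2°C | Item 37.5°C or above |
|---|---|---|
| Cough, 37.3°C, nothing else | case | not a case |
| Cough, 37.3°C, headache | case | case |
| Cough, sore throat, 37.3°C | case | case |

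The cell decides mainly when there is a single respiratory symptom and no other systemic symptom.

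**4. Can it move a date?** Yes. SAP Step 3 has the start date "set as either the positive RT-PCR date or the earliest eligible symptom onset date, whichever occurs earlier". Take 37.3°C on day 13, 37.5°C and cough on day 14, and a positive test on day 15. With the SAP threshold the start is day 14. With the protocol threshold, treating the raised temperature as one continuing symptom, it is day 13. If the SAP's 14-day start is applied to this date, the protocol threshold moves the case out of the counted period.

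**5. What is one case worth?** Planned arm sizes are 50 (Cohort A) and 52 (Cohort B). One case is 1/50 = 2.0% or 1/52 = 1.9%. For Clopper-Pearson 95% limits, the upper limit at zero cases is 1 − 0.025^(1/n). At one case the lower limit is 1 − 0.975^(1/n) and the upper is the 97.5% quantile of Beta(2, n − 1).

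| Cases | n = 50 | n = 52 |
|---|---|---|
| 0 | 0% (0 to 7.11%) | 0% (0 to 6.85%) |
| 1 | 2.0% (0.05 to 10.65%) | 1.9% (0.05 to 10.26%) |

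The documents give no ILI rate and no temperature distribution, so the expected number of such cases cannot be computed.

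**6. The SAP's other rules against protocol 10.3.7 and 9.5.2:**
- Laboratory: the SAP asks for "RT-PCR performed at the Global Central Laboratory and/or a local certified laboratory within 7 days of onset of protocol-defined ILI". The laboratory part is narrower in wording than the protocol's acceptance of any setting.
- Seven-day link: not in 10.3.7, but it follows the protocol's swab timing (Section 8.3.7.1 and Table 1, footnote l).
- Overlap: the SAP requires "The occurrence of any 2 or more respiratory symptoms that overlap for at least 1 day". The protocol attaches concurrency only to the respiratory-plus-systemic route.
- Fourteen-day start: the SAP summaries of confirmed ILI begin 14 days after injection, a limit absent from 9.5.2 and 10.3.7. The SAP's definition sentence itself covers the whole study period, and earlier positives are tabulated as test results.

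**The case against.** The strongest reply is that protocol 9.5.4 leaves exploratory analyses to the SAP, that SAP Section 1 lets the SAP govern, and that the CSR, which is not available here, could still disclose the difference. This stands for what will be run and for where disclosure may happen. It does not make a 37.5°C threshold the protocol's, or the statement in SAP Section 4 correct. Supplying derivation detail is not the same as replacing a number that the protocol gives.

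The delegation argument does carry weight for the other SAP rules. A reader might infer from step 6 four further undeclared changes of the same standing. The documents do not support that. Protocol 10.3.7 gives no time link between test and symptoms, and an analysis needs one; the seven-day rule takes it from the protocol's own swab schedule. The overlap rule makes the symptom combination computable. The 14-day start is a reporting period. Only the laboratory wording is plainly narrower, and nothing in the documents shows that tests from a non-certified source exist.

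A reader might also infer that the SAP count can only equal or fall below the protocol's. That holds only if 10.3.7 is read with no time link at all. SAP Step 1 accepts symptom onset up to 7 days after a positive sample, whereas the protocol's swab rule has the swab follow onset. If the protocol is linked through that rule, the SAP can count a case that the protocol would not. Step 4 shows that the temperature cell alone can also shift a case across a boundary.

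Finally, the absence of an ILI entry in the SAP's summary of major changes might be taken as evidence of non-disclosure. That table records differences between SAP versions, not differences from the protocol.

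**Conclusion.** The contradiction on temperature is established: the same label, two thresholds, and a declaration of no change. As written, SAP Table 8 does not implement protocol 10.3.7 for readings above 37.2°C and below 37.5°C. The effect is about 2 percentage points per affected participant per arm, assuming planned arm sizes. The number affected is unknown and may be zero.

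Severity is minor. The analysis is exploratory, descriptive, unpowered and limited to Part 1, and one rule applies in every arm. RT-PCR results and ILI symptoms are also listed, so individual cases can be inspected. A reader might fear a wider effect, but the documents do not show one. The Part 1 Per Protocol Set excludes on RT-PCR-confirmed infection, not on ILI, so the secondary immunogenicity analyses do not depend on Table 8. Table 8 is used only in the ILI derivation, so the primary safety summaries do not either. Non-disclosure is shown for the SAP alone.

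**What to change.** Reconcile protocol 10.3.7 with SAP Table 8 by one of two routes:
1. Derive the summary labelled protocol-defined ILI with the protocol's temperature item.
2. Keep the SAP threshold, give the summary a different label, and list the difference with its date and reason in SAP Section 4 or the CSR.

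Under either route, use the same entry to note that the SAP's laboratory wording is narrower than the protocol's. It should also note that the seven-day link, the overlap rule for two respiratory symptoms and the 14-day reporting start are SAP operating rules not stated in protocol 10.3.7 or 9.5.2.

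The cost is small: one rerun or one label, plus a short entry. The first route assumes that the ILI symptom eCRF holds temperature as a number. If it holds only a yes/no item at a fixed threshold, only relabelling and declaring is possible. Timing also favours the second route. Protocol Section 2 puts Part 1 enrolment in April to May 2023. Assuming a last injection by 31 May 2023, Day 181 falls on 27 November 2023 and its window closes 14 days later, on 11 December 2023. That is before the eCRF date of 31 May 2024 cited in SAP Section 1, so Part 1 data collection had probably ended before this SAP version.

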#### **2.6.5.3. SARS-CoV-2 Infection**

Symptomatic COVID-19 is defined by the presence of one of the CDC-listed symptoms (CDC, 2020) and a positive RT-PCR test on a respiratory sample. SARS-CoV-2 should be suspected if the participant experiences any one of the symptoms listed below lasting at least 48 hours (except for fever and/or respiratory symptoms) (CDC, 2020) :

- Fever (temperature  $\geq 38.0^{\circ}\text{C}$  [ $100.4^{\circ}\text{F}$ ]) or chills (of any duration, including  $\leq 48$  hours)
- Cough (of any duration, including  $\leq 48$  hours)
- Shortness of breath and/or difficulty breathing (of any duration, including  $\leq 48$  hours)
- Fatigue
- Muscle or body aches
- Headache
- New loss of taste and/or smell
- Sore throat, congestion, or runny nose
- Nausea or vomiting

- Diarrhea

Symptomatic COVID-19 is defined by the presence of one of the CDC-listed symptoms (CDC, 2020) and a positive RT-PCR test on a respiratory sample.

If the participant had known exposure to COVID-19 (eg, exposure to someone with a confirmed case of COVID-19), it will be captured in the COVID-19 exposure form, and the participant will continue to follow all remaining study assessments as scheduled. Likewise, participants with a confirmed case of COVID-19 will continue to follow all remaining study assessments as scheduled.

The following summaries will be provided:

- The number and percentage of participants with an RT-PCR test results (Positive, Negative, Not Applicable, Missing) at Baseline will be summarized by vaccination group (as defined in Section 2.6.1).
- The number and percentage of participants with an RT-PCR test results (Positive, Positive and  $\leq$ 14 Days After Injection, Positive and  $>$  14 Days After Injection, Negative, Not Applicable, Missing) excluding Baseline will be summarized by vaccination group (as defined in Section 2.6.1).
- The number and percentage of participants with, and the number of events of RT-PCR confirmed SARS-CoV-2 Infection, and RT-PCR Symptomatic SARS-CoV-2 Infection within the period starting from 14 days post-injection up through EoS will be summarized by time period.
- A listing presenting the RT-PCR test results for SARS-CoV-2 infection will be provided.
- A listing presenting the symptom assessment for SARS-CoV-2 infection will be provided.

## 2.6.6. Other Exploratory Endpoints

Transcriptomic and genomic samples will be part of the optional biomarker assessment. Exploratory assessments may include assessment of biomarkers for safety, reactogenicity, and inflammation. Serologic markers of disease severity, immune response to SARS-CoV-2 or influenza, RT-PCR of nasal swab samples, genetic sequences of SARS-CoV-2 or influenza

strains isolated from participants' samples, and genomic and transcriptomic samples may also be evaluated. Analyses and reporting of these endpoints will be covered in a separate analysis plan if applicable.

## **2.6.7. Planned Analyses**

### **2.6.7.1. Interim Analysis**

An interim analysis of safety, reactogenicity, and immunogenicity is planned after all the participants in Cohort A and B have completed the Day 29 visit. The interim analysis as of completion of Day 29 will be performed by the study statistician and programmers. The group-level unblinded summary data of the Day 29 interim analyses may be reviewed by the Sponsor project team for safety monitoring and/or clinical development planning purposes for the mRNA-1083 project. More details will be documented in the study Data Blinding Plan.

In addition, another interim analysis for reactogenicity data up to Day 8 only may be performed after all the participants in Cohort A and B have completed the Day 8 visit. The potential interim analysis as of completion of Day 8 may be performed by an independent team of unblinded statistician and programmers. More details will be documented in the study Data Blinding Plan.

### **2.6.7.2. Final Analysis**

The final analysis will be performed after all the participants in both Cohort A and Cohort B have completed the Day 181/EoS visit.

### 3. Part 2

#### 3.1. Study Objectives

##### 3.1.1. Primary Objectives

The primary objectives are:

- To evaluate the safety and reactogenicity of study intervention administration across study treatment arms
- To evaluate the humoral immune responses to vaccine-matched strains for influenza and SARS-CoV-2 across study treatment arms at Day 29

##### 3.1.2. Secondary Objectives

The secondary objective is:

- To evaluate the humoral immune responses to vaccine-matched strains for influenza and SARS-CoV-2 across study treatment arms at all evaluable humoral immunogenicity time points

##### 3.1.3. Exploratory Objectives

The following exploratory objectives may be assessed:

- To evaluate the humoral immune responses to vaccine-mismatched strains for influenza and SARS-CoV-2 across study treatment arms
- To evaluate the humoral immune responses against vaccine-matched and vaccine-mismatched strains for influenza and SARS-CoV-2 across study treatment arms
- To further characterize the immune response to influenza and SARS-CoV-2 across study treatment arms

### 3.2. Study Endpoints

#### 3.2.1. Primary Endpoints

- Solicited local and systemic ARs through 7 days after injection

- Unsolicited AEs through 28 days after injection
- Unsolicited Severe AEs through 28 days after injection
- Unsolicited MAAEs from Day 1 to Day 181/EoS
- Unsolicited AESIs from Day 1 to Day 181/EoS
- SAEs from Day 1 to Day 181/EoS
- Unsolicited AEs leading to discontinuation from Day 1 to Day 181/EoS
- GMT and GMFR at Day 29 compared to Day 1 by HAI assay for influenza and by PsVNA for SARS-CoV-2
- Influenza: Percentage of participants with seroconversion, defined as a Day 29 titer **CCI** if Baseline is **CCI** or a 4-fold or greater rise if Baseline is **CCI** in anti-HA antibodies measured by HAI assay
- SARS-CoV-2: Percentage of participants with seroresponse, defined as a Day 29 titer  $\geq 4$ -fold if Baseline is  $\geq \text{LLOQ}$  or  $\geq 4 \times \text{LLOQ}$  if Baseline titer is  $< \text{LLOQ}$  in nAb titers measured by PsVNA

### 3.2.2. Secondary Endpoints

- GMT and GMFR at all evaluable time points compared to Day 1 by HAI for influenza and PsVNA for SARS-CoV-2
- Influenza: Percentage of participants with seroconversion, as defined in Section 3.2.1
- SARS-CoV-2: Percentage of participants with seroresponse, as defined in Section 3.2.1

### 3.2.3. Exploratory Endpoints

- GMT and GMFR at all evaluable time points compared to Day 1 by HAI for influenza and PsVNA for SARS-CoV-2
- Influenza: Percentage of participants with seroconversion, as defined in Section 3.2.1
- SARS-CoV-2: Percentage of participants with seroresponse, as defined in Section 3.2.1

- GMT and GMFR at all evaluable time points compared to Day 1 by alternative methods, including, but not limited to: microneutralization assay for influenza or ligand-binding assay for SARS-CoV-2
- Frequency, specificities, or other endpoints to be determined for the further characterization of immune responses

### **3.3. Study Design**

#### **3.3.1. Overall Study Design**

[figure not shown]
**Part 2** of the study will be a Phase 2 randomized, stratified, observer-blind, active-control study to evaluate the safety, reactogenicity, and immunogenicity of mRNA-1083 compositions and dose levels compared with active-control vaccines mRNA-1010, mRNA-1283.815, mRNA-1273.815, and licensed active-control vaccine, Fluarix in healthy adults  $\geq 18$  to  $<50$  years of age. Approximately 520 participants  $\geq 18$  to  $<50$  years of age will be enrolled. Participants will be randomized (in equal allocation ratio) into the investigational treatment arms, stratified by influenza vaccine status in the most recent influenza season (received or not received since Sept 2023). Table 9 lists the details of study cohorts and dose levels for study vaccine administration. All participants will receive a single IM injection of study intervention administered in a deltoid muscle on Day 1.

**Table 9 Study Arm(s) and Interventions (Part 2)**

Part 2 Arm: ( $\geq 18$ to $<50$ years), n=40/arm, 520 total	Intervention	Total mRNA Dose ( $\mu$ g) a	Intervention Type
1	mRNA-1083 CCI	CCI	IP
2	mRNA-1083		IP
3	mRNA-1083		IP
4	mRNA-1083		IP
5	mRNA-1083		IP
6	mRNA-1083		IP
7	mRNA-1083		IP
8	mRNA-1083		IP
9	mRNA-1010 CCI		Non-IP experimental comparator
10	mRNA-1010		Non-IP experimental comparator
11	mRNA-1283.815		Non-IP experimental comparator
12	mRNA-1273.815		Licensed vaccine comparator
13	Fluarix	-	Licensed vaccine comparator

All participants of the study will participate in a Screening period (up to 28 days before Day 1), treatment period (single dose of vaccine on Day 1), and a follow-up period (up to 6 months after vaccination). The study schema is presented in Figure 2 Study Schema. Please refer to the Part 2 Schedule of Activities (SoA) available in Appendix A.

**Figure 2 Study Schema (Part 2)**

Abbreviation: mRNA = messenger ribonucleic acid

### 3.3.2. Statistical Hypotheses

See Section 2.3.2 for details.

